#### **11.1.2.1 Visit 2 (Day 1)**

The following evaluations will be performed:

- Review inclusion/exclusion criteria.
- Check subject discontinuation criteria.
- Check IMP suspension criteria (for further details, see Section 9.3.2).
- Record physical examination outcome (changes from the previous visit).
- Record vital signs (once at least 15 minutes before the infusion and once at least 15 minutes after the infusion).
- Record triplicate 12-lead ECG (once at least 15 minutes before the infusion and once at least 15 minutes after the infusion).
- Perform continuous real-time ECG monitoring (for details, see Section 12.3.4).
- Record concomitant medications and therapies.
- Ask the subject to complete pain intensity assessments.
- Ask the subject to complete the BPI interference scale.
- Ask the subject to complete the PDI.
- Ask the subject to complete the EQ-5D-5L.
- Ask the subject to complete the PASS.
- Ask the subject to complete the CES-D.
- Ask the subject to complete the WPAI: CRPS (US sites only).
- Collect medical resources utilization and health economics data (US sites only).
- Complete the assessment of the signs and symptoms of CRPS.
- Take blood for safety laboratory.
- Collect urine for central safety laboratory urinalysis and local dipstick evaluation (calculate urinary ACR).
- Take blood (in the morning) for bone turnover marker evaluation.
- Perform a urine  $\beta$ -HCG pregnancy test (for women of child-bearing potential).
- Record adverse events (based on subject reporting before, during, and after infusion).
- Allocate to IMP (using IRT system).
- Administer IMP (for further details, see Section 10.2).

#### **11.1.2.2 Visit 3 (Day 4; $\pm 1$ day)**

The following evaluations will be performed:

- Check subject discontinuation criteria.
- Check IMP suspension criteria (for further details, see Section 9.3.2).

- 
- Record vital signs (once at least 15 minutes before the infusion and once at least 15 minutes after the infusion).
  - Record triplicate 12-lead ECG (once at least 15 minutes before the infusion and once at least 15 minutes after the infusion).
  - Perform continuous real-time ECG monitoring (for details, see Section 12.3.4).
  - Record concomitant medications and therapies.
  - Ask the subject to complete pain intensity assessments.
  - Take blood for safety laboratory.
  - Collect urine for central safety laboratory urinalysis and local dipstick evaluation (calculate urinary ACR).
  - Perform a urine  $\beta$ -HCG pregnancy test (for women of child-bearing potential).
  - Record adverse events.
  - Administer IMP (for further details, see Section 10.2).

#### 11.1.2.3 Visit 4 (Day 7; $\pm 1$ day)

The following evaluations will be performed:

- Check subject discontinuation criteria.
- Check IMP suspension criteria (for further details, see Section 9.3.2).
- Record vital signs (once at least 15 minutes before the infusion and once at least 15 minutes after the infusion).
- Record triplicate 12-lead ECG (once at least 15 minutes before the infusion and once at least 15 minutes after the infusion).
- Perform continuous real-time ECG monitoring (for details, see Section 12.3.4).
- Record concomitant medications and therapies.
- Ask the subject to complete pain intensity assessments.
- Take blood for safety laboratory.
- Collect urine for central safety laboratory urinalysis and local dipstick evaluation (calculate urinary ACR).
- Perform a urine  $\beta$ -HCG pregnancy test (for women of child-bearing potential).
- Record adverse events.
- Administer IMP (for further details, see Section 10.2).

#### 11.1.2.4 Visit 5 (Day 10; $\pm 1$ day)

The following evaluations will be performed:

- Check subject discontinuation criteria.
- Check IMP suspension criteria (for further details, see Section 9.3.2).
- Record vital signs (once at least 15 minutes before the infusion and once at least 15 minutes after the infusion).

- 
- Record triplicate 12-lead ECG (once at least 15 minutes before the infusion and once at least 15 minutes after the infusion).
  - Perform continuous real-time ECG monitoring (for details, see Section 12.3.4).
  - Record concomitant medications and therapies.
  - Ask the subject to complete pain intensity assessments.
  - Take blood for safety laboratory.
  - Collect urine for central safety laboratory urinalysis and local dipstick evaluation (calculate urinary ACR).
  - Perform a urine  $\beta$ -HCG pregnancy test (for women of child-bearing potential).
  - Record adverse events.
  - Administer IMP (for further details, see Section 10.2).

### **11.1.3 Follow-up period**

#### **11.1.3.1 Visit 6 (Week 2; $\pm 2$ days)**

The following evaluations will be performed:

- Check subject discontinuation criteria.
- Record vital signs.
- Record triplicate 12-lead ECG.
- Record concomitant medications and therapies.
- Ask the subject to complete pain intensity assessments.
- Take blood for safety laboratory.
- Collect urine for central safety laboratory urinalysis.
- Take blood (in the morning) for bone turnover marker evaluation.
- Record adverse events.

#### **11.1.3.2 Visit 7 (Week 6; $\pm 7$ days)**

The following evaluations will be performed:

- Check subject discontinuation criteria.
- Record vital signs.
- Record concomitant medications and therapies.
- Ask the subject to complete pain intensity assessments.
- Ask the subject to complete the PGIC.
- Ask the subject to complete the BPI interference scale.
- Ask the subject to complete the PDI.
- Ask the subject to complete the EQ-5D-5L.
- Ask the subject to complete the PASS.
- Ask the subject to complete the CES-D.
- Complete the assessment of the signs and symptoms of CRPS.

- Take blood for safety laboratory.
- Collect urine for central safety laboratory urinalysis.
- Take blood (in the morning) for bone turnover marker evaluation.
- Record adverse events.

**11.1.3.3 Visit 8 (Week 12; ±7 days)**

The following evaluations will be performed:

- Check subject discontinuation criteria.
- Record physical examination outcome (changes from the previous visit).
- Record vital signs.
- Record concomitant medications and therapies.
- Ask the subject to complete pain intensity assessments.
- Ask the subject to complete the PGIC.
- Ask the subject to complete the BPI interference scale.
- Ask the subject to complete the PDI.
- Ask the subject to complete the EQ-5D-5L.
- Ask the subject to complete the PASS.
- Ask the subject to complete the CES-D.
- Complete the assessment of the signs and symptoms of CRPS.
- Take blood for safety laboratory.
- Collect urine for central safety laboratory urinalysis.
- Take blood (in the morning) for bone turnover marker evaluation.
- Record adverse events.
- Prescribe tetracycline and dispense tetracycline dosing diary to US subjects undergoing a bone biopsy for recording the intake of tetracycline.

**11.1.3.4 Visit 9 (Week 26; ±15 days)**

A single bone biopsy will be obtained from the iliac crest, following tetracycline double-labeling, in a subset of subjects (from US sites only). The biopsy should be scheduled to be performed 26 weeks after the first administration of IMP. Biopsies will be obtained from approximately 20 subjects to obtain approximately 15 evaluable biopsy specimens.

The following evaluations will be performed:

- Check subject discontinuation criteria.
- Record physical examination outcome (changes from the previous visit).
- Record vital signs.
- Record triplicate 12-lead ECG.
- Record concomitant medications and therapies.
- Ask the subject to complete pain intensity assessments.

- 
- Ask the subject to complete the PGIC.
  - Ask the subject to complete the BPI interference scale.
  - Ask the subject to complete the PDI.
  - Ask the subject to complete the EQ-5D-5L.
  - Ask the subject to complete the PASS.
  - Ask the subject to complete the CES-D.
  - Ask the subject to complete the WPAI: CRPS (US sites only).
  - Collect medical resources utilization and health economics data (US sites only).
  - Complete the assessment of the signs and symptoms of CRPS.
  - Take blood for safety laboratory.
  - Collect urine for central safety laboratory urinalysis.
  - Take blood (in the morning) for bone turnover marker evaluation.
  - For women of child-bearing potential allocated to treatment after the first 100 subjects have been allocated, perform a urine  $\beta$ -HCG pregnancy test.
  - For all subjects allocated to treatment after the first 100 subjects have been allocated, collect subject trial card.
  - Perform bone imaging (DXA and MRI will be performed in a subset of approximately 30 subjects [from US sites only]).
  - Record adverse events.
  - Collect tetracycline dosing diary from US subjects undergoing a bone biopsy.

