### 1.1.1 Flow diagram summary of the trial

### 1.1.2 Brief description of the sequence and duration of all trial periods

There will be an enrollment period lasting up to 60 days, a treatment period consisting of 4 infusions over 10 days, and a follow-up period of approximately 50 weeks (Visit 6 [Week 2] through Visit 11 [Week 52]). The subjects are expected to be in the trial for approximately 60 weeks (14 months). See Section 1.1.1 for a summary of the trial as a flow diagram and Section 1.6 for a tabular schedule of events.

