- t) The subject card is to be returned at the final visit or at the Early Termination Visit in the case of early discontinuation from the trial.
- u) It is planned to perform bone densitometry (DXA) and MRI in a subset of 30 subjects.
- v) A single bone biopsy will be obtained from the iliac crest, following tetracycline double-labeling, in a subset of subjects. The biopsy should be scheduled to be performed 26 weeks after the first administration of IMP. It is planned to obtain approximately 15 evaluable bone biopsy samples from approximately 20 subjects.
- w) At US sites only.
- x) For US subjects undergoing bone biopsy only.

$\beta$ -HCG = beta-human chorionic gonadotropin, BPI = Brief Pain Inventory, CES-D = Center for Epidemiological Studies Depression Scale, CRPS = complex regional pain syndrome, DXA = dual-energy X-ray absorptiometry, ECG = electrocardiogram, eGFR = estimated glomerular filtration rate, EQ-5D-5L = EuroQol-5 dimension 5 level, IASP = International Association for the Study of Pain, IMP = investigational medicinal product, MRI = magnetic resonance imaging, NRS = numerical rating scale, PASS = Pain Anxiety Symptom Scale, PDI = Pain Disability Index, PGIC = Patient Global Impression of Change, WPAI = Work Productivity and Activity Impairment Questionnaire.

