#### **11.1.3.6 Visit 11 (Week 52; ±15 days)**

The following evaluations will be performed:

- Record physical examination outcome (changes from the previous visit).
- Record vital signs.
- Record triplicate 12-lead ECG.
- Record concomitant medications and therapies.
- Ask the subject to complete pain intensity assessments.
- Ask the subject to complete the PGIC.
- Ask the subject to complete the BPI interference scale.
- Ask the subject to complete the PDI.
- Ask the subject to complete the EQ-5D-5L.
- Ask the subject to complete the PASS.
- Ask the subject to complete the CES-D.
- Ask the subject to complete the WPAI: CRPS (US sites only).
- Collect medical resources utilization and health economics data (US sites only).
- Complete the assessment of the signs and symptoms of CRPS.
- Take blood for safety laboratory.
- Collect urine for central safety laboratory urinalysis.
- Take blood (in the morning) for bone turnover marker evaluation.
- Perform a urine  $\beta$ -HCG pregnancy test (for women of child-bearing potential).
- Collect subject trial card.
- Record adverse events.

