## **11.4 Subject trial cards**

Subjects who are enrolled in the trial will receive a subject trial card (the time of card distribution is given in Section 1.6). The trial card will list the following information:

- Name of the subject and a statement that he/she is currently participating in a clinical trial.
- Trial code
- Dates of all individual visits.
- Name of the principal investigator for that trial site.
- Contact (telephone) number at the trial site.

The card will be collected at the last visit.

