**8.2.2 Further definitions**

Term	Definition
Baseline	
For this single-arm non-randomized trial, baseline is the last observation (scheduled or unscheduled) before first IMP administration, unless specified otherwise. In general, baseline is the value recorded at Visit 2.
 
For physical examinations, a general assessment will be done at Visit 1, and at all subsequent visits (scheduled or unscheduled) the change compared to the previous visit will be assessed.
 
For bone imaging assessments, a separate baseline visit must be scheduled during the enrollment period for subjects undergoing bone densitometry and magnetic resonance imaging procedures.

Early termination visit	Subjects who discontinue the follow-up period before their last planned visit should undergo an Early Termination Visit with procedures identical to Visit 11. If a subject discontinues then, the data recorded under Visit 11 in the eCRF are treated as data belonging to the Early Termination Visit.
Follow-up period	The follow-up period starts after the treatment period and ends at Visit 11.
Follow-up completers	Subjects completing Visit 11 in the follow-up period. Intermittent missed visits in the follow-up period are allowed and do not affect the follow-up completion status.
Investigational Medicinal Products (IMP)	Neridronic acid in the form of sodium neridronate hemi hydrate 108 mg for intravenous infusion (equivalent to 100 mg neridronic acid) supplied in 8 mL of excipients. The full contents of a single ampule or vial (8 mL) will be diluted in 500 mL normal saline and administered by slow intravenous infusion (240 minutes [maximum 260 minutes]) at Visit 2, Visit 3, Visit 4 and Visit 5, resulting in a total dose of neridronic acid 400 mg.
On-treatment-period	For the purpose of this trial, the on-treatment period starts at the first IMP administration (included) and continues until the date (included) when the subject leaves the trial, i.e., at Visit 11 for trial completers, and otherwise at the Early Termination Visit for discontinued subjects. This is based on the persistence in bone and potentially prolonged effect of neridronic acid.

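### The Visit 9 (Week 26) procedure list still has sites take back the trial card from subjects allocated after the first 100, although follow-up now runs to Week 52 with no split by allocation order

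*Protocol*

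**What the plan says.** The Visit 9 list in Protocol 11.1.3.4 includes the bullet "For all subjects allocated to treatment after the first 100 subjects have been allocated, collect subject trial card".

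Three other places in the current protocol also say when the card comes back:

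- Section 1.6, footnote t: "The subject card is to be returned at the final visit or at the Early Termination Visit".
- Section 11.1.3.6, the Visit 11 (Week 52) list: "Collect subject trial card", with no condition attached.
- Section 11.4: "The card will be collected at the last visit".

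On the length of follow-up, Protocol 1.1.2 describes one follow-up period of about 50 weeks, from Week 2 to Week 52, and does not divide subjects by order of allocation. SAP 8.2.2 agrees: "The follow-up period starts after the treatment period and ends at Visit 11".

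Section 11.4 lists what the card shows. This includes "Name of the subject and a statement that he/she is currently participating in a clinical trial" and "Contact (telephone) number at the trial site", as well as the trial code, the visit dates and the principal investigator's name.

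**The concern.** For a subject who stays in the trial, Week 26 is not the last visit. An instruction to take the card then cannot be squared with three instructions to take it at the end of participation. It would also leave nothing to collect at Visit 11 from most of the trial.

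What is at stake is practical. This is a safety trial with a year of follow-up, and after Week 26 subjects are still expected to get in touch with the site. Women are told to make contact at once if they suspect pregnancy (11.3.4). Subjects are asked to report dental pain, gum problems and planned dental work (11.3.3), and thigh, hip or groin pain (8.2). Several drugs and procedures stay prohibited throughout the trial (1.4.3), so a clinician outside the trial has reason to know that the patient is in it. The card is one way to provide the telephone number and that information. Staff are likely to work from the visit list on the day, so a wrong line there deserves removal even when the general rule is right elsewhere.

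**Working it through.** The plan has no statistical figure to reproduce here. The check compares the current text and then counts the subjects whom the wording covers.

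**Step 1. Is Week 26 the final visit for anyone who continues?** No. Protocol 1.1.2 and SAP 8.2.2 both end follow-up at Visit 11. Protocol 11.1.3.5 and 11.1.3.6 set out Visit 10 (Week 39) and Visit 11 (Week 52) without limiting either to the first 100 subjects.

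**Step 2. Set the card instructions side by side.**

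| Place in the protocol | Who | When |
|---|---|---|
| 11.1.3.4, Visit 9 list | Subjects allocated after the first 100 | Week 26 |
| 1.6, footnote t | All | Final or Early Termination Visit |
| 11.1.3.6, Visit 11 list | All | Week 52 |
| 11.4 | All | Last visit |

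The last three agree with each other and with Step 1. The first agrees with none of them.

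**Step 3. Could the Visit 9 bullet serve subjects who leave at Week 26?** No. It is not limited to them. A subject who leaves early has an Early Termination Visit with the Visit 11 procedures (9.3.3.1), and those already include card collection.

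**Step 4. Where does the bullet come from?** Amendment 01 (19.1) set out to follow every subject for up to 52 weeks. Its log shows that the sentence making Visit 9 the last visit for later subjects was struck from 11.1.3.4, as was the matching sentence in footnote t. The card bullet stayed. The log only explains the origin; the conflict itself lies within the current text.

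**Step 5. How many subjects does the wording cover?** Protocol 1.5.1 plans about 290.

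- 290 − 100 = 190
- 190 / 290 = 65.5%, or about 66%

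**Step 6. How early would the card go?**

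- In weeks: 52 − 26 = 26.
- In planned visit days (SAP 20.1.1.14): 365 − 182 = 183 days. Each visit has a window of ±15 days, so the range is 183 − 30 = 153 to 183 + 30 = 213 days.
- Scheduled visits remaining after Visit 9: Visits 10 and 11, so two.

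**The case against.** The strongest reply accepts the conflict and disputes its weight.

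**The right answer is easy to find.** Three places state it, and the unconditional Visit 11 bullet presupposes that subjects still hold the card at Week 52. A site that noticed the clash could resolve it. This stands, and it is a main reason to rate the point low.

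**Other provisions partly replace the card.** Section 11.1 asks sites to remind subjects two days before visits. The reminder is about fasting, but it also tells the subject that a visit is due, so losing the visit dates matters little. Section 4.3 recommends telling the subject's healthcare provider at enrollment about participation, with the trial code, the principal investigator's name and a site telephone number. This also stands, though only in part. It applies in countries where it is applicable, needs the subject's written agreement, and reaches one provider rather than whoever treats the subject in an emergency. Consent materials are not part of the text reviewed, so subjects may hold the number in another form.

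**The figure of 190 is a ceiling.** This is right. It counts subjects to whom the wording applies, not cards taken early. Dropout before Week 26 lowers it, as does any site that follows the other three instructions, and the documents quantify neither. A reader might infer that about two thirds of the trial lost the card or their contact with the site. The documents do not support that.

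**The adjacent pregnancy-test bullet.** It carries the same condition about the first 100 subjects, so a reader might infer a second defect, or that the plan leaves Week 26 testing unsettled. That cannot be asserted. The schedule-of-events rows for the pregnancy test and the card are not in the text available for this review, and the pregnancy row may state who is tested at Visit 9. SAP 15.2.1 names Visit 9 among the test visits, which is compatible with the protocol as written.

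**Conclusion.** The contradiction is real and lies in current operative text: the Visit 9 card bullet conflicts with the follow-up schedule and with three other instructions on the same card. Nothing in the documents reconciles it.

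Its size is modest. The wording covers up to about 190 of about 290 planned subjects, who would give up the card about 26 weeks early with two visits left. That rests on the planned sample size, on all subjects after the first 100 reaching Visit 9, and on sites following the Visit 9 list; the documents show nothing about the last of these.

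A reader might also infer that subjects allocated later are followed only to Week 26, or that the safety data are shortened for them. The documents do not support this. Follow-up, the visit schedule and the SAP definitions all run to Visit 11, and only the handling of the card is out of step. No endpoint, dosing decision or analysis is affected. The point is worth correcting because subjects still in safety follow-up would keep the site number and the statement of participation, and because correcting it is nearly free.

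**What to change.** Delete the card-collection bullet from Protocol 11.1.3.4 at the next amendment. Collection then happens only at Visit 11 or the Early Termination Visit, as the rest of the protocol already says.

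The cost is one deleted line. It adds no procedure and no data item, and the SAP needs no change.

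When making that edit, the sponsor should check the condition about the first 100 subjects in the adjacent pregnancy-test bullet against the pregnancy-test row of the schedule of events. No change to that bullet is recommended here.

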#### **11.1.3.5 Visit 10 (Week 39; $\pm$ 15 days)**

The following evaluations will be performed:

- Check subject discontinuation criteria.
- Record physical examination outcome (changes from the previous visit).
- Record vital signs.
- Record concomitant medications and therapies.
- Ask the subject to complete pain intensity assessments.
- Ask the subject to complete the PGIC.
- Ask the subject to complete the BPI interference scale.
- Ask the subject to complete the PDI.
- Ask the subject to complete the EQ-5D-5L.
- Ask the subject to complete the PASS.
- Ask the subject to complete the CES-D.
- Complete the assessment of the signs and symptoms of CRPS.
- Take blood for safety laboratory.
- Collect urine for central safety laboratory urinalysis.
- Take blood (in the morning) for bone turnover marker evaluation.

- Record adverse events.

#### **11.1.3.6 Visit 11 (Week 52; ±15 days)**

The following evaluations will be performed:

- Record physical examination outcome (changes from the previous visit).
- Record vital signs.
- Record triplicate 12-lead ECG.
- Record concomitant medications and therapies.
- Ask the subject to complete pain intensity assessments.
- Ask the subject to complete the PGIC.
- Ask the subject to complete the BPI interference scale.
- Ask the subject to complete the PDI.
- Ask the subject to complete the EQ-5D-5L.
- Ask the subject to complete the PASS.
- Ask the subject to complete the CES-D.
- Ask the subject to complete the WPAI: CRPS (US sites only).
- Collect medical resources utilization and health economics data (US sites only).
- Complete the assessment of the signs and symptoms of CRPS.
- Take blood for safety laboratory.
- Collect urine for central safety laboratory urinalysis.
- Take blood (in the morning) for bone turnover marker evaluation.
- Perform a urine  $\beta$ -HCG pregnancy test (for women of child-bearing potential).
- Collect subject trial card.
- Record adverse events.

